4. Anorectal manometry and magnetic evoked potential tests are performed at baseline and may be performed at the 3-month follow-up assessment. Questionnaires to assess FI severity, FIQOL, and psychological tests are given at the same intervals.

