#### Table of Measures for all participants

Schedule of assessments*	Screening Baseline Randomi		Randomize	3 mo	6 mo	12 mo	18 mo	24 mo
Socio-demographics and examination	Х							
Bowel diary, including BSFS		х	х	х	Х	х		Х
Endoanal ultrasound		X**		X*** (INJ arm only)				
Balloon Evacuation Test (BET)		X**						
Anorectal manometry (ARM)		X**		X***				
Magnetic Evoked Potential (MEP)		X**		X***				
Fecal Incontinence Severity Scale (FISS)		X	x	х	X	X		X
Fecal Incontinence Quality of Life (FIQOL)		Х	x	x	Х	X		X
PHQ-12 Somatization scale			x	Х	X	Х		Х
PROMIS Anxiety-7			Х	Х	X	Х		Х
PROMIS Depression-8			X	Х	X	Х		Х
PROMIS Self-Efficacy Symptom Management			x	х	X	Х		X
Assessment of AEs, SAEs		Х	x	х	X	X	х	х
Cost (treatments, # of visits, out of pocket)		X	x	х	X	x	X	X
Work Productivity and Impairment (WPAI)		X	x	х	X	x	X	X
EuroQol 5D (EQ-5D)		X	X	Х	X	Х	Х	Х
Burden of Treatment Questionnaire		X	x	x	X	x	x	X
GI Symptom Questionnaire		X						
ABLe	3 		X	Х	X	Х		X
Continence Rating			х	Х	X	Х		Х

\* Additionally, participants will complete the Credibility/ Expectancy Questionnaire (CEQ) each time that they start one of the study interventions. So, all study participants will complete the CEQ when they start EMM all randomized participants will complete the CEQ when they start BIO or INJ as a randomized treatment, and participants will complete the CEQ if they select BIO, INJ or SNS when they are identified as non-responders to the randomized treatment at the 3-month follow-up assessments.

\*\* The endoanal ultrasound, BET, ARM and MEP may be conducted at the randomization visit, if not done at Baseline but must be conducted prior to randomization. If an imaging study (US or MRI) was performed in the previous 12 months to assess the sphincters, then this need not be repeated at Baseline if the sphincters appeared normal and there has been no history of anorectal trauma, surgical procedures, or vaginal deliveries in the intervening period between the imaging exam and study participation.

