- 8. Characterization of Enhanced Medical Treatment Durability of improvement and predictors of response: The primary purpose of treating all patients with an EMM run-in is to be able to exclude patients who do not require more costly interventions. However, we will take advantage of the opportunity provided by this run-in study to identify predictors of response to EMM and to assess the durability of improvements. EMM will not be "usual care" but will follow a written protocol that is intended to optimize EMM, which is why we label this enhanced medical management. Patients who are treatment responders at the end of the EMM run-in will be scheduled for 3-month follow-up, and those who are no longer treatment responders at 3 months follow up will be offered an opportunity to be randomized to one of the 2 treatments at this point. However, those who remain responders to EMM at 3 months follow up will continue to be followed for an additional 21 months. All patients, regardless of their outcomes at the end of EMM, will be encouraged to continue using the treatment approaches learned during the EMM phase. Participants, whether determined to be EMM responders or not, will be asked at the end of the 1-month EMM period and then also at the 3-; 6-; 12-; and 24-month follow-up assessments if they are continuing to adhere to these treatment approaches (pelvic floor exercises and medication).

Event	Window for event
Screening	N/A
Baseline	To be completed no more than 6 weeks after Screening Visit.
EMM – start	EMM should start 0 days – 4 weeks from the completion of the Baseline diary.
EMM - Check-in Calls	
 
Call 1: 3 – 5 business days after starting EMM
 
14-day call: 2 business days before - 2 business days after the 14th day from the start of EMM
 

Randomization in Medidata	Randomization in Medidata EDC should occur 4 weeks - 6 weeks after the start of EMM. Note :
	
 
The Randomization Visit may occur anytime between the end of EMM and Treatment Initiation.
 

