#### 3.1 Event Windows:

	• But , all requirements for randomization eligibility must be completed before randomization in Medidata.
Treatment initiation (Time 0) for first randomized intervention (BIO, INJ)	
 
Randomized treatment should start 0 days to 4 weeks after randomization in Medidata.
 
Note:
 
If treatment is initiated on the same day as the Randomization Visit, all randomization requirements (questionnaires and procedures) should be completed before treatment initiation.
 
The Time 0 date used to determine subsequent events dates in the Medidata EDC will be determined as follows: 
 
Time 0 for BIO = Date of Train Session 1
 
Time 0 for INJ = Date of the first injection
 
Time 0 for EMM responders = Date the randomization eligibility CFR is completed in Medidata (that is, date when participant is deemed to be ineligible for a randomized intervention as considered a responder to EMM).
 
For any participant who does not respond to EMM but who is also not randomized for any other reason, the Time 0 used to determine the schedule for the follow-up assessments will also be the date on which the randomization eligibility CRF is completed in Medidata.
 
 
 

Biofeedback (BIO) therapy (5 x 1- hour visits, with an optional 6 th )	Each Biofeedback Train session should be spaced with a minimum interval of 2 days and a maximum interval of 10 days from the previous session, with no more than two sessions in a calendar week. Preferred is one training session per week.
Injection (INJ) – 6- week follow-up	1 week before – 2 weeks after the target date determined from Time 0
3-month follow-up	1 week before – 3 weeks after the target date determined from Time 0
6-month follow-up assessment	1 week before – 3 weeks after the target date determined from Time 0
12-month follow- up assessment	1 week before – 3 weeks after the target date determined from Time 0
18-month follow- up assessment	1 week before – 3 weeks after the target date determined from Time 0
24-month follow- up assessment	3 weeks before – 3 weeks after the target date determined from Time 0
Optional treatment - initiation	Optional additional treatment initiation should occur within 0 days to 4 weeks after the 3-month visit post randomization.

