#### 5.5 Feasibility Survey

In Year 1 of the U34 planning grant, we conducted two feasibility surveys to inform us whether sufficient numbers of subjects would be willing to be randomized to a 3-arm treatment study. In the first survey, we recruited 164 individuals through an internet registry who reported experiencing FI at least twice each month. The anonymous internet survey gave brief descriptions of BIO, SNS, and INJ including published reports of their effectiveness, safety, and cost. These subjects were then asked to rate the effectiveness and safety of each treatment on a 0-10 scale from "definitely not" to "yes, definitely". They rated their willingness to undergo each treatment on a 0-10 scale from "definitely not" to "yes, definitely". The 164 respondents to this survey included 112 females (68% of total sample), average age was 43 years, and average FISS severity score was 8 with 119 (73%) scoring in the moderate to severe range of FI severity. When asked to rate their willingness to enroll in a study in which they would be randomly assigned to one of these three treatments, 32% rated their willingness as 8 or greater on the 0-10 scale. When asked about each treatment separately they were significantly more willing to try BIO than INJ, and significantly more willing to try INJ than SNS. They rated these three treatments as equally effective but BIO was perceived as significantly safer than INJ, and INJ was perceived as significantly safer than SNS. Concerns expressed about the safety of SNS included infection risk, use of electricity, and possible nerve damage.

The second feasibility survey was carried out in the 4 clinical settings where this study would take place. From 40 to 51 patients with established diagnoses of FI participated at each site (total n=187). The proportion who would be willing to be randomized with a confidence rating of at least 8/10 was 40%. Patients who were unwilling to be randomized to this three-arm study most commonly listed safety concerns (62%) or unequal costs as reasons for their reluctance to be randomized. The data from these two surveys suggest that approximately 32% to 40% of eligible patients would be willing to be randomized. This is consistent with our assumption (see Figure 3) that 1 in 3 patients screened will be eligible and willing to be randomized.

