Assessment of Disease-Specific Quality of Life. Change from baseline to 3 months, and to 6 through 24 months in the FI Quality of Life (FIQOL) scale will be analyzed using methods described for the analysis of FI severity.

Assessment of Anxiety, Depression, and Self-Efficacy for Managing Symptoms. Change from baseline to 3 months, and to 6 through 24 months in these Patient Reported Outcomes Measurement Information System (PROMIS) scales will be analyzed using methods described for assessment of FI severity.

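### The PROMIS baseline is not defined, and Section 3.1 lets the PROMIS and PHQ-12 reference scores be collected after the patient knows the assigned arm

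*Combined protocol and SAP*

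**What the plan says.** For the anxiety, depression and self-efficacy scales, the outcome in Section 8.2 is "Change from baseline to 3 months, and to 6 through 24 months in these Patient Reported Outcomes Measurement Information System (PROMIS) scales". The methods are those given for FI severity. They model change with treatment group, clinical site and sex as independent variables. No baseline score enters as a covariate, and no visit is named as the PROMIS baseline.

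In the synopsis Table of Measures and again in Table 2, the row for "PROMIS Anxiety-7" has no mark under Screening or Baseline. Its marks are at Randomize and at 3, 6, 12 and 24 months. The rows for PROMIS Depression, PROMIS Self-Efficacy and PHQ-12 are the same. FISS and FIQOL are marked at both Baseline and Randomize.

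Item 4 of the synopsis schema places manometry and evoked potentials at baseline and, optionally, at 3 months. It then adds: "Questionnaires to assess FI severity, FIQOL, and psychological tests are given at the same intervals".

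On timing, the Section 3.1 event windows put randomization in Medidata 4 to 6 weeks after the start of EMM and state: "The Randomization Visit may occur anytime between the end of EMM and Treatment Initiation". They continue: "Randomized treatment should start 0 days to 4 weeks after" randomization. Requirements for randomization eligibility must be complete before randomization. For the case where treatment starts on the day of the Randomization Visit, "all randomization requirements (questionnaires and procedures) should be completed" before treatment is initiated.

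**The concern.** Elsewhere in the protocol, baseline means the period before EMM. For PROMIS no score is scheduled there, so the reader must guess that the Randomize score is the reference. The schema line points to a different schedule.

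The timing is the more important half. The trial is open to patients, and Section 3.0 (item 7) expects many of them not to find the two treatments equally credible. It relies on randomization to balance expectancy. Randomization cannot balance a score that is taken after the patient has been told the arm. If that score serves as the reference for change, any reaction to the assignment becomes part of the estimated treatment effect.

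PHQ-12 has the same schedule. Section 4.3.1 names it as a moderator, and Section 8.3 examines predictors through interactions with treatment group. Such a variable should be fixed before allocation.

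**Working it through.** The documents give no PROMIS sample size, effect or SD, so there is no plan figure to reproduce. The check is of schedule and wording, followed by an illustration of size.

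**1. Which score is the reference?** Both tables agree that the first PROMIS and PHQ-12 scores are at Randomize. Agreement across two tables makes a text-extraction fault unlikely. Schema item 4, read literally, puts the psychological tests at baseline and 3 months. That conflicts with the tables at baseline and also omits the scheduled 6, 12 and 24 months. Section 8.2 does not settle it.

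**2. How late can that score be?** From the Section 3.1 windows, in weeks from EMM start:
- Randomization: week 4 to 6.
- Treatment initiation: 0 to 4 weeks after randomization, so at the latest 6 + 4 = week 10.
- Randomization Visit: from end of EMM up to treatment initiation, so up to 4 weeks after allocation.

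**3. Does anything force the questionnaires before allocation?**
- Eligibility requirements must come first, but PROMIS and PHQ-12 are not among the Section 5.1 criteria.
- The synopsis footnote requires ultrasound, BET, ARM and MEP before randomization even when done at the Randomization Visit. It does not cover questionnaires.
- The one sentence naming questionnaires sets its limit at treatment initiation, and only for same-day visits.

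No rule clearly requires them before allocation.

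**4. What would a reaction do?** Let g be the between-arm difference in reaction at the Randomization Visit, in SD units, f the share of visits held after allocation, and rho the correlation between that score and the 3-month score. Assume the reaction has gone by 3 months. Change is the 3-month score minus the reference score, so the between-arm difference in change is biased by f × g in magnitude. Treatment, site and sex in the model do not remove this.

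For scale, take 97 per arm (Section 5.4) and a two-sided 5% test:
- SE = sqrt(2(1 − rho)) × sqrt(2/97), which is 0.144 for rho = 0.5 and 0.111 for rho = 0.7.
- With g = 0.2 and f = 0.5, bias = 0.10 SD. The ratio of bias to SE is 0.10/0.144 = 0.70, or 0.10/0.111 = 0.90.

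| g | f | Bias (SD) | Error rate, rho 0.5 | Error rate, rho 0.7 |
|---|---|---|---|---|
| 0.1 | 0.25 | 0.025 | 5.3% | 5.6% |
| 0.2 | 0.5 | 0.10 | 10.7% | 14.6% |
| 0.3 | 1 | 0.30 | 55.1% | 77.0% |

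The values of g, f and rho are assumptions; none is in the documents. Section 5.4 expects 78 and 92 patients at 3 months. That leaves the bias unchanged and lowers the error rates somewhat.

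Adding the contaminated score as a covariate would shrink the bias to rho × f × g (0.05 or 0.07 SD in the middle row) but not remove it.

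**The case against.** The strongest reply is that the text can be read the other way. Section 3.1 calls the questionnaires randomization requirements. Sections 4.2.1 and 4.2.4 give FISS and FIQOL at the end of EMM and cite Table 2, where the matching column is Randomize. Table 9 schedules a closing EMM visit, and the diary in that column must be in the EDC before randomization because it decides eligibility. Many sites may therefore collect everything beforehand, and the procedure manuals, which are not part of these documents, may say so. This stands as far as it goes: late collection is permitted, not shown. The wording remains ambiguous, and sites may follow either reading.

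Several stronger inferences are tempting, and the documents do not support them:
- **That PROMIS change cannot be derived, or that all 194 patients lack a baseline.** A pre-treatment score is scheduled for every randomized patient, and change from it can be computed. What is missing is the definition.
- **That no earlier score exists for anyone.** EMM responders who relapse are randomized after a 3-month assessment at which PROMIS and PHQ-12 are already scheduled.
- **That assignment to INJ raises anxiety, which then falls and flatters INJ.** The Section 5.5 internet survey found that "they were significantly more willing to try BIO than INJ" and that BIO was seen as safer. But it concerned a three-arm study including SNS, found the treatments rated equally effective, and did not measure anxiety after assignment. The direction is conjecture.
- **That randomized arm contrasts are distorted at every follow-up.** For 6 to 24 months, Section 8.2 gives descriptive intervals for 3-month responders by arm and for non-responders by chosen combination. These are not whole-arm contrasts.
- **That a post-EMM starting point biases the comparison.** Everyone randomized has been through EMM before allocation. The different origin from FISS and FIQOL affects interpretation, not the arm contrast.

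Even at 3 months, Section 8.2 specifies intervals per arm and no formal between-arm test. The synopsis does state a between-arm difference in psychological symptoms as a secondary outcome, so a comparison is intended.

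**Conclusion.** The point holds as a gap in definition combined with a timing rule that is too loose. The PROMIS baseline is not named, one synopsis line conflicts with both tables, and the windows allow the scheduled pre-treatment PROMIS and PHQ-12 scores to be taken up to 4 weeks after allocation in an open trial.

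The consequence is confined to three secondary scales, mainly their 3-month arm comparison, and to an exploratory moderator. The three primary outcomes are untouched. The possible bias equals the share of late visits times the between-arm reaction. Neither factor is in the documents, so the table shows sensitivity and is not an estimate. The conclusion rests on reading Section 3.1 as permitting late questionnaires. If every site already collects them before allocation, only the definition and the schema line need correcting. The change is worth making because it is cheap and because analysis cannot fully repair a reference score taken after allocation.

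**What to change.** - **Section 3.1 and Table 2:** require PROMIS, PHQ-12 and the other questionnaires in the Randomize column to be completed before randomization in Medidata, preferably enforced as a condition in the EDC. The emailed links described in Section 7.2.3 make this possible without an extra visit.
- **Section 8.2:** define PROMIS change as change from that pre-allocation score and state that it is a post-EMM origin, unlike the pre-EMM baseline available for FISS and FIQOL. State which score applies to relapsed EMM responders. Name the same pre-allocation value for PHQ-12 in the Section 8.3 models.
- **Synopsis schema, item 4:** reconcile it with the two schedule tables.
- **Patients already enrolled:** compare questionnaire and randomization dates, flag scores dated after allocation, report how many there are per arm, and repeat the analysis without them.

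The cost is a short wording change and a date check, with no new assessment. The small downside is that randomization waits until the questionnaires are done at any site that now holds the visit afterwards.

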#### 8.3 Analysis of Secondary Aims

*Identify predictors of treatment response to each intervention.* Generalized linear modeling will be used to identify baseline variables which are significant independent predictors of responder status at 3 months. Candidate independent variables in these models include (a) demographic variables (e.g., sex, age, race, ethnicity, education); (b) clinical history variables (e.g., FI frequency, volume, duration, and association with urgency and diarrhea); and (c) baseline pelvic floor physiology (e.g., anal canal resting pressure, squeeze pressure, duration of squeeze, rectal sensory threshold for first sensation and urgency, maximum tolerable volume, structural integrity of anal sphincters assessed by ultrasound, and integrity of the pelvic floor innervation by trans-sacral and trans-lumbar magnetic evoked potentials) and other moderator variables described in the protocol. Differences in predictors of response among the treatment groups will be assessed by evaluating interaction terms for the predictors and treatment group. Secondary analyses evaluating predictors of treatment response at other time points and predictors of other secondary outcomes will be conducted using similar methods.

Investigate the mechanistic basis for treatment success for each intervention. General linear modeling will be used to identify measures associated with change from baseline to 3 months in FI frequency. The independent variables to be tested are anal squeeze pressures, rectal sensory thresholds, rectal maximum tolerable volume, trans-lumbar and trans-anal magnetic evoked potential, stool consistency measure by the Bristol Stool Form Scale, and adherence to protocol. Differences in predictors among the treatment groups will be assessed by evaluating interaction terms for the predictors and treatment group.

*Evaluate treatment combinations.* To assess the effectiveness of allowing non-responders to choose an additional treatment at 3 months, we will estimate 95% confidence intervals for the number of responders in each treatment-order combination at 6, 12, and 24 months using a Wilson Score interval. Confidence intervals will be compared descriptively.

Assess the efficacy and durability of enhanced medical treatment and identify patient characteristics that predict treatment response. The proportion of responders will be calculated at the end of EMM and at 3-, 6-, 12-, and 24-month follow-up. A longitudinal generalized linear model will be constructed to predict treatment response based on time and clinical site; the model will account for the lack of independence between multiple measures assessed over time on the same study participant by modeling the within-participant covariance structure. Participants who are non-responders to EMM at 3 months will continue to be classified as non-responders at 6, 12, and 24 months. Participants without a valid bowel diary will be classified as non-responders at that time point, and those who initiate off-study treatment for FI after EMM will be classified as non-responders at each subsequent visit/assessment. Using this model, we will compare response rates at the end of EMM to response rates at 3, 6, 12, and 24 months. We will also calculate 95% confidence intervals for the percentage of participants reporting AEs during EMM. Costs of EMM will be estimated and compared to costs of the other study interventions using methods described for cost of care analysis. The predictors of response to EMM at baseline, 3, 6, 12, and 24 months will be explored using generalized linear modeling.

*Cost- Effectiveness Analysis.* We will estimate the impact of each intervention on quality-adjusted life-years (QALYs). QALYs are summary measures of morbidity and mortality that typically range from 0 to 1 over a full year, where 1 represents perfect health. QALY estimates will be obtained from the EQ-5D; annual QALY measures will be calculated. We will assess the average cost per QALY gained for each intervention and the incremental cost per QALY gained by comparing the interventions ordered from lowest to highest QALY gains (i.e., comparing the intervention with medium effectiveness to the intervention with lowest effectiveness and the intervention with highest effectiveness to the intervention with medium effectiveness).

